8.7 PK Analysis

All PK analyses will be performed for subjects in the PK Analysis set with evaluable serum PK samples. Serum KRN23 will be summarized descriptively at each time point.

8.8 General Safety Analysis

All safety analyses will be performed on the Safety Analysis set at each milestone analysis. The treatment Extension Analysis Set might also be used for safety analysis at the final analysis. General safety will include dosing summary, AEs, treatment related AEs, SAEs, events to monitor, prior and concomitant medication, laboratory measurements including chemistry, hematology, and urinalysis parameters, GFR, amylase, HAHA, pregnancy test and vital signs. No hypothesis testing is planned for safety data.

8.8.1 Dosing Summary

The total dose administered and the subjects with dose adjustment and the reasons for dose adjustment will be summarized by treatment groups by visits for the safety analysis set.

8.8.2 Adverse Events

Reported adverse event (AE) terms are coded to MedDRA (version 18.1). All reported events will appear in AE listings, however only TEAEs will be summarized. TEAEs are defined as AEs occurring or worsened in severity on or after the first dose date of IP.

The following AEs will be summarized at each milestone analysis:

- All TEAEs
- Related TEAEs
- TEAE by severity
- Events to monitor:
 - Injection site reactions
 - Immunogenicity
 - Hyperphosphataemia
 - Ectopic mineralization
 - Restless legs syndrome
- Grade 3/4 TEAEs
- Serious TEAEs
- Serious related TEAEs
- TEAEs resulting in discontinuation
- Fatal TEAEs.

The incidence and frequency of AEs will be summarized by System Organ Class (SOC), Preferred Term (PT). Events to monitor will be summarized by PT. Injection site reactions (ISR) will be listed for PT, seriousness, severity, outcome, relationship to study drug, and onset time from IP administration.

Listings will be created for AEs which lead to death, discontinuation of treatment, and SAEs.

8.8.3 Prior and Concomitant Medications

Both prior and concomitant medications will be coded by drug name and therapeutic class using WHO Drug dictionary, version 2015 September or newer.

Prior medication will be summarized by therapeutic class and preferred term at week 48 analysis.

At each specific milestone analysis, concomitant medications will be summarized by therapeutic class and preferred term.

8.8.4 Safety Lab Parameters

The descriptive statistics will be provided for lab safety parameters (chemistry, hematology, and urinalysis parameters, serum 25(OH)D, FGF23, lipase, amylase, eGFR). Observed values and change from baseline will be presented.

In addition, a shift table will be provided for amylase. The following categories will be used for serum amylase:

- No Grade
- Grade 1: >ULN to 1.5 x ULR
- Grade 2: >1.5 to 2 x ULR
- Grade 3: >2 to 5 x ULR
- Grade 4: > 5 x ULR

Individual and mean (\pm SE) over time plots may be presented for selected safety lab parameters.

Listings of the lab safety parameters will be provided.

8.8.5 HAHA

Antibody (human anti-human antibody [HAHA]) results will be summarized by the baseline and post-baseline testing results. Each subject positive for antibody will be listed with titer (if available), the cumulative dose of KRN23 up to the time of the positive antibody test, the time since the first exposure to KRN23, and the latest dose of KRN23 before the positive antibody test.

8.8.6 Physical Examination

Physical exam results will include the assessment of general appearance; head, eyes, ears, nose, and throat; the cardiovascular, dermatology, lymphatic, respiratory, gastrointestinal, musculoskeletal, genitourinary, neurological systems. All physical examination assessments will be listed.

8.8.7 Pregnancy Test

A subject level listing for pregnancy test results will be created for those who had a positive pregnancy test.

8.8.8 Vital Signs

Systolic blood pressure, diastolic blood pressure, temperature, respiratory rate and heart rate and their changes from baseline over time will be summarized. If the subject has taken 2 measurements of BP separated by 15 min at the same scheduled visit per the protocol amendment 1, the mean of the 2 measurements of the blood pressure at the visit will be used for analysis.

8.9 Ectopic Mineralization Safety Analysis

Ectopic mineralization safety data includes renal ultrasound, ECG, ECHO, serum calcium, phosphorus, intact parathyroid hormone (iPTH), urinary calcium and creatinine.

The observed values and changes from baseline in the ectopic mineralization labs (serum calcium etc.) will be summarized. Listings containing the ectopic mineralization safety parameters will be provided.

8.9.1 Renal Ultrasound

Renal ultrasound will be conducted with findings of nephrocalcinosis graded on a 5-point scale and by a central reader. These results will be summarized by time point. Furthermore, a grade shift table summarizing changes from baseline by time point will also be created.

The number and percentage of subjects with nephrolithiasis observed in the cortical collecting duct will be summarized by time point. A shift table summarizing changes from baseline by time point will be created.

A listing of renal ultrasound nephrocalcinosis scores, the presence or absence of nephrolithiasis in the cortical collecting duct and the radiologist's comments will also be provided.

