#### **7.3.3.1 Stopping Rules**

No formal statistical stopping criteria will be applied for this study. A Data Monitoring Committee (DMC) will be constituted for Studies UX023-CL303 and UX023-CL304 and will act in an advisory capacity to monitor the safety of KRN23 on a routine basis until the end of the Treatment Period (Week 48) (Section 7.6.7). The DMC may provide advice to Ultragenyx to aid in the determination of whether study enrollment should be paused or if the study should be stopped. If the Sponsor deems it appropriate to restart the trial following an internal safety review, this will be done only following approval by Regulatory Authorities.

During Treatment Extension Periods I and II, safety data will be reviewed by the Ultragenyx Study Safety Review Team (SSRT) as described in Section 8.5.4.6.

Individual subjects who experience any unexpected and possibly, probably, or definitely drug-related SAEs (Section 8.5.3) that represent a change in the nature or an increase in frequency of the serious event from their prior medical history will be assessed as to whether the subject will continue on the study.

Individual subjects will be monitored for ectopic mineralization (Section 7.5.3). If new or clinically significant worsening in mineralization is considered clinically meaningful by the investigator and/or sponsor and related to study drug, the subject will be discontinued from the study.

Regulatory Authorities, as well as the Institutional Review Board (IRB)/Ethics Committee (EC) will be informed should unexpected and possibly, probably, or definitely drug-related SAEs occur. A full clinical evaluation of the event will be performed in order to make a decision regarding what actions to take, including whether to recommend stopping the study. Regulatory Authorities, as well as IRBs/ECs, will be informed if the study is paused or stopped.

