7 DATA SCREENING AND ACCEPTANCE

7.1 Handling of Missing and Incomplete Data

Missing clinical outcome data can occur for multiple reasons, including missed subject visits and measures with missing item scores. Missing and incomplete data will be identified through a review of tables and listings for this study. Missing and incomplete data will be identified for investigation, and possible resolution, by Data Management prior to the study database lock.

For all analyses, missing data will be treated as missing, unless otherwise specified. When a change from baseline is assessed, only subjects with a baseline and at least one post-baseline measurement will be included in the analysis.

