8.9.2 ECG

Summary statistics for the absolute measurements and changes from Baseline for selected ECG parameters including the following intervals: QT, QTcF - Fridericia's Correction Formula, the time elapsed from the onset of atrial depolarization to the onset of ventricular depolarization (PR), RR duration, and time elapsed for depolarization of the ventricles (QRS) will be provided.

ECG parameters will also be summarized by the maximum post-baseline value and maximum change from baseline using the following categories based on International Conference on Harmonisation (ICH) E14 ([ICH 2005](#)).

Categories for ECG Results

ECG Parameter	Categories for Baseline and Maximum Post-Baseline Value	Categories for Maximum Change from Baseline Value
QTcF	≤450, >450-≤480, >480-≤500 and >500 msec	≤30, >30-≤60 and >60 msec

The normality or abnormality of the ECG tracing will be summarized using shift tables of numbers of subjects who have a normal/abnormal ECG tracing by visits.

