8.9.3 ECHO

ECHO data will be centrally read to assess for evidence of ectopic mineralization in the heart and aorta and to evaluate for signs of LVH or cardiac dysfunction. Descriptive statistics for the various continuous ECHO measurements (e.g., left ventricular mass index, etc.) will be at the scheduled time points and will include the change from baseline value. The summary of the descriptive statistics will be displayed by visit. The categorical summaries for the subjects with change from baseline ≥ 2 in ectopic mineralization score will be performed. Shift tables will be provided for categorical ECHO measurements (e.g. ectopic mineralization score, aortic and mitral valve regurgitation).

A listing of all ECHO parameters will also be created.

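### Nephrocalcinosis is tabulated only by time point, so no planned table counts subjects whose centrally read grade ever worsened, and the ECHO mineralization tables have no stated time basis.

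*SAP*

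**What the plan says.** **Renal ultrasound (SAP 8.9.1).** On the five-point nephrocalcinosis grade, assigned by a central reader: "These results will be summarized by time point". Then: "Furthermore, a grade shift table summarizing changes from baseline by time point will also be created". Nephrolithiasis has the same by-time-point layout. A listing of scores is planned.

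**ECHO (SAP 8.9.3).** The sentence "The summary of the descriptive statistics will be displayed by visit" follows the text on continuous measurements and refers to those. Two further sentences cover the mineralization score: "The categorical summaries for the subjects with change from baseline ≥ 2 in ectopic mineralization score will be performed" and "Shift tables will be provided for categorical ECHO measurements (e.g. ectopic mineralization score, aortic and mitral valve regurgitation"). Neither gives a visit or an any-time rule.

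**ECG (SAP 8.9.2).** A per-subject extreme is planned here: "ECG parameters will also be summarized by the maximum post-baseline value and maximum change from baseline", with categories for QTcF.

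**Removal (Protocol 7.3.3.1).** If mineralization is new or has worsened to a clinically significant degree, and is judged clinically meaningful and "related to study drug, the subject will be discontinued from the study".

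**Missing data (SAP 7.1).** "For all analyses, missing data will be treated as missing, unless otherwise specified".

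**Early termination and unscheduled reads (SAP 7.2).** These are mapped to the nearest scheduled visit. If a scheduled reading exists for that visit, it is the one summarized. Listings and shift tables keep every reading.

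**The concern.** Ectopic mineralization is named in the safety objective, and Protocol 7.4.3 singles out nephrocalcinosis when it explains the dosing strategy. The natural question is how many treated subjects had a worse grade at any time on drug. A table by time point does not answer it. Each visit has its own denominator of subjects scanned at that visit, and a subject can leave that denominator because of the outcome being tabulated.

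At stake is the long-term statement on mineralization. A Week 72 or Week 96 table with no worsening could mean that nobody worsened, or that those who did were no longer being scanned. The reader would have to go to the listings to tell which.

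**Working it through.** The plan states no rate, precision or sample-size figure for mineralization, so there is no figure of its own to reproduce. The check is a reading of the planned tables, followed by an illustration on assumed counts.

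**Step 1. Which planned output counts each treated subject once, by centrally read grade?**

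| Output | Counts each subject once? | Based on the central grade? |
|---|---|---|
| Nephrocalcinosis summary and shift, SAP 8.9.1 | No, by time point | Yes |
| Ectopic mineralization adverse events, SAP 8.8.2 with Protocol 7.6.5 | Yes, at least one occurrence | No, investigator-reported |
| Adverse events leading to discontinuation, SAP 8.8.2 | Yes | No, investigator-reported |
| ECHO mineralization score: count with change of 2 or more, and shift, SAP 8.9.3 | Not stated | Yes, for the ECHO score |
| Listings, SAP 8.9.1 and 8.9.3 | Not a summary | Yes |

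For nephrocalcinosis no row has both properties. Protocol 7.5.3.11 makes an imaging change an adverse event only where the investigator thinks it appropriate, so a one-grade rise on the central read need not reach the adverse event tables.

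**Step 2. Example by direct counting.** Inputs: 14 subjects (SAP 3.1) and scans at Weeks 24, 48, 72 and 96 (Protocol 7.5.3.5). Assumed: one new worsener at each of Weeks 24, 48 and 72 and none at Week 96, with persistent worsening.

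| Visit | By-visit table, each worsener then removed | By-visit table, nobody removed | Ever worsened |
|---|---|---|---|
| Week 24 | 1/14 = 7.1% | 1/14 = 7.1% | 1/14 = 7.1% |
| Week 48 | 1/13 = 7.7% | 2/14 = 14.3% | 2/14 = 14.3% |
| Week 72 | 1/12 = 8.3% | 3/14 = 21.4% | 3/14 = 21.4% |
| Week 96 | 0/11 = 0% | 3/14 = 21.4% | 3/14 = 21.4% |

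Wilson 95% interval for 3/14, with p = 0.2143, n = 14, z = 1.96:
- centre = (p + z²/2n)/(1 + z²/n) = 0.3515/1.2744 = 0.2758
- half-width = z·√(p(1−p)/n + z²/4n²)/(1 + z²/n) = 0.2001
- interval 7.6% to 47.6%

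For 0/11 the Wilson interval is 0% to 25.9%.

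**Step 3. Range over assumed risks.** Let h be the risk of new worsening per interval and q the share of worseners removed, with persistent worsening. Let w be the fraction never worsened and s the fraction worsened and still on study, starting at w = 1 and s = 0. At each of the four visits:
- new = h·w
- share shown = (s + new)/(w + s)
- then w falls by new, and s rises by (1 − q)·new

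Ever worsened = 1 − (1 − h)⁴.

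| h | Week 96 shown, q = 0 | q = 0.5 | q = 1 | Ever worsened |
|---|---|---|---|---|
| 2% | 7.8% | 5.0% | 2.0% | 7.8% |
| 5% | 18.5% | 12.3% | 5.0% | 18.5% |
| 10% | 34.4% | 24.1% | 10.0% | 34.4% |

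With no removals and persistent worsening there is no gap. With every worsener removed, the Week 96 table shows only the new cases of the last interval.

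**The case against.** Four objections carry weight.

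**The removed cases are not hidden.** Removal applies only to worsening judged clinically meaningful and drug-related, and those are the cases most likely to be reported as adverse events. Ectopic mineralization is an event to monitor, nephrocalcinosis and nephrolithiasis are among its terms (SAP Appendix 4), and discontinuations due to adverse events are tabulated. A reader might infer that no planned table counts anyone who ever worsened. The documents do not support that. What stands is narrower: no table does so on the centrally read grade.

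**The readings are kept.** A removed subject appears at the visit where the worsening was seen, an ultrasound is scheduled at early termination, and all readings go into the shift table and listings. This is a real safeguard, but the shift table is still by time point and does not add subjects up across visits. In the by-time-point summary, a worse early termination read can give way to a scheduled read mapped to the same visit.

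**ECHO.** A reader might infer that ECHO mineralization is also tabulated only visit by visit. SAP 8.9.3 attaches that layout to the continuous measurements. The count of subjects with a change of 2 or more may already be an any-time count. The text is unclear on this and needs a stated time basis.

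**The size is hypothetical, and the QTcF contrast is not a contradiction.** Both are right. Without removals, a gap arises only if worsening reverts. The documents offer no support for reversal: Protocol 5.2.2 reports that reversibility was not established in animals. Part of any one-visit change would be reader noise. SAP 8.9.2 bases its QTcF categories on ICH E14, and nothing obliges the sponsor to use that format for ultrasound. The contrast shows only that a per-subject extreme is already used in the same chapter.

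**Conclusion.** The concern holds in a limited form. For nephrocalcinosis, the plan has no summary that counts each treated subject once by worst centrally read grade, and the removal rule means that later by-visit tables can understate worsening. For ECHO the fault is a missing time basis.

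A reader might go further and infer that the Week 72 and Week 96 tables are biased towards no progression. That depends on removals, or on worsening that reverts, and the documents give a rate for neither. The 0/11 against 3/14 example assumes three worseners, all removed. If nobody is removed and worsening persists, the by-visit table already shows the full count.

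Severity is modest. There are 14 subjects in a single arm, no hypothesis tests are planned on safety data (SAP 8.8), and the listings let a reader rebuild the count by hand. The change is still worth making, because it gives a cumulative result on a named part of the safety objective.

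**What to change.** In SAP 8.9.1, add for the Safety Analysis Set:
- a shift from baseline to the worst post-baseline centrally read nephrocalcinosis grade, using all scheduled, unscheduled and early termination reads, with each subject counted once;
- the number and percentage of subjects who ever worsened by at least one grade;
- beside these, the shift from baseline to the last available read.

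In SAP 8.9.3, state that the count with a change of 2 or more and the mineralization-score shift are also given on the worst post-baseline value.

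Keep the by-visit tables. The discontinuation rule in the protocol is not affected.

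The cost is some SAP wording and a few extra summaries from images already read centrally, with no new data. The downside is that reader noise can push a worst-value summary upwards. The last-read shift helps to show how much of the worsening persisted.

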8.9.2 ECG

Summary statistics for the absolute measurements and changes from Baseline for selected ECG parameters including the following intervals: QT, QTcF - Fridericia's Correction Formula, the time elapsed from the onset of atrial depolarization to the onset of ventricular depolarization (PR), RR duration, and time elapsed for depolarization of the ventricles (QRS) will be provided.

ECG parameters will also be summarized by the maximum post-baseline value and maximum change from baseline using the following categories based on International Conference on Harmonisation (ICH) E14 ([ICH 2005](#)).

Categories for ECG Results

ECG Parameter	Categories for Baseline and Maximum Post-Baseline Value	Categories for Maximum Change from Baseline Value
QTcF	≤450, >450-≤480, >480-≤500 and >500 msec	≤30, >30-≤60 and >60 msec

The normality or abnormality of the ECG tracing will be summarized using shift tables of numbers of subjects who have a normal/abnormal ECG tracing by visits.

8.9.3 ECHO

ECHO data will be centrally read to assess for evidence of ectopic mineralization in the heart and aorta and to evaluate for signs of LVH or cardiac dysfunction. Descriptive statistics for the various continuous ECHO measurements (e.g., left ventricular mass index, etc.) will be at the scheduled time points and will include the change from baseline value. The summary of the descriptive statistics will be displayed by visit. The categorical summaries for the subjects with change from baseline ≥ 2 in ectopic mineralization score will be performed. Shift tables will be provided for categorical ECHO measurements (e.g. ectopic mineralization score, aortic and mitral valve regurgitation).

A listing of all ECHO parameters will also be created.

10 APPENDICES

[figure not shown]
Appendix 1: Summary of Efficacy Endpoint and Analysis

Test / Instrument	Endpoint	Type	Time points for Assessment	Statistical Analysis
Bone Biopsy	The primary endpoint is the percent change from baseline in osteoid volume/bone volume (OV/BV) at Week 48 based on analysis of iliac crest bone biopsies.	Primary Efficacy Endpoints	Baseline, 48/ET	Descriptive Summary and T-Test (or Sign Test)
Serum Phosphorus	The proportion of subjects achieving mean serum phosphorus levels above 2.5 mg/dL at the mid-point of the dose interval as averaged across dose cycles between baseline and Week 24.	Key Secondary Efficacy Endpoints	Screening, Baseline, Week 1, 2, 4, 6, 12,14,20,21, 22, 24,28, 36, 48, 60, 70, 72, 84, 94, 96, ET.	Descriptive Summary and Wilson Confidence Interval
Bone Biopsy	Percent changes from baseline in additional histomorphometric parameters – including osteoid thickness (O.Th), osteoid surface/bone surface (OS/BS), and mineralization lag time (MLt)	Secondary Efficacy Endpoints	Baseline, 48/ET	Descriptive Summary and T-Test (or Sign Test)
Bone Biopsy	Changes from baseline in MAR, MS/BS, BFR and additional measures of bone formation and remodeling	Secondary Efficacy Endpoints	Baseline, 48/ET	Descriptive Summary
Serum Phosphorus	Proportion of subjects achieving mean serum phosphorus levels above 2.5 mg/dL at the end of the dosing cycle, as averaged across dose cycles	Secondary Efficacy Endpoints	Screening, Baseline, Week 1, 2, 4, 6, 12,14,20,21, 22, 24,28, 36, 48, 60, 70, 72, 84, 94, 96, ET.	Descriptive Summary
	Mid-point of dosing cycle: mean change from baseline and percent change from baseline averaged across dose cycles through Week 24	Secondary Efficacy Endpoints		Descriptive Summary
	End of dosing cycle: mean change from baseline averaged across dose cycles	Secondary Efficacy Endpoints		Descriptive Summary
	Cumulative exposure: Time Adjusted area under the curve (AUC)	Secondary Efficacy Endpoints		Descriptive Summary

[figure not shown]
Test / Instrument	Endpoint	Type	Time points for Assessment	Statistical Analysis
PD	Change from baseline over time in serum intact FGF23, ALP, 1,25(OH)2D; and urinary phosphorus, TRP, TmP/GFR, and FEP	Secondary Efficacy Endpoints	Screening, Baseline, Week 1, 2, 4, 12,20,21, 22, 24,36, 48, 60, 72, 84, 94, 96, ET.	Descriptive Summary , GEE Model
Biomarker	Change and percent change from baseline over time in bone biomarker, including BALP, CTx, P1NP, and osteocalcin	Secondary Efficacy Endpoints	Baseline, week 12, 24, 48, 72, 96 and ET.	Descriptive Summary , GEE Model
X-Ray	Number of post-baseline healed, partial healed pseudofractures from baseline active pseudofractures; Number of subjects who have active pseudofractures at baseline and healed, partial healed post-baseline pseudofractures	Exploratory Efficacy Endpoints	Baseline, week 12, 24, 36, 48 and ET.	Descriptive Summary , GEE Model
BPI	Change from baseline in:	Exploratory Efficacy Endpoints	Screening, Baseline, week 12, 24, 36, 48, 72, 96 and ET.	Descriptive Summary , GEE Model
	Worst Pain			
	Pain Severity			
	Pain Interference			
BFI	Change from Baseline in:	Exploratory Efficacy Endpoints	Screening, Baseline, week 12, 24, 36, 48, 72, 96 and ET.	
	Worst Fatigue			
	Global Fatigue Score			

Appendix 2: Brief Pain Inventory

Appendix 3: Brief Fatigue Inventory

Appendix 4: Events to Monitor

Injection site reactions: based on HLT “Injection site reaction”

Category	PT
Injection site reaction	Embolia cutis medicamentosa
Injection site reaction	Injected limb mobility decreased
Injection site reaction	Injection site abscess
Injection site reaction	Injection site abscess sterile
Injection site reaction	Injection site anaesthesia
Injection site reaction	Injection site atrophy
Injection site reaction	Injection site bruising
Injection site reaction	Injection site calcification
Injection site reaction	Injection site cellulitis
Injection site reaction	Injection site coldness
Injection site reaction	Injection site cyst
Injection site reaction	Injection site dermatitis
Injection site reaction	Injection site discharge
Injection site reaction	Injection site discolouration
Injection site reaction	Injection site discomfort
Injection site reaction	Injection site dryness
Injection site reaction	Injection site dysaesthesia
Injection site reaction	Injection site eczema
Injection site reaction	Injection site erosion
Injection site reaction	Injection site erythema
Injection site reaction	Injection site exfoliation
Injection site reaction	Injection site extravasation
Injection site reaction	Injection site fibrosis
Injection site reaction	Injection site granuloma
Injection site reaction	Injection site haematoma
Injection site reaction	Injection site haemorrhage
Injection site reaction	Injection site hyperaesthesia
Injection site reaction	Injection site hypersensitivity
Injection site reaction	Injection site hypertrichosis
Injection site reaction	Injection site hypertrophy
Injection site reaction	Injection site hypoaesthesia
Injection site reaction	Injection site induration
Injection site reaction	Injection site infection
Injection site reaction	Injection site inflammation
Injection site reaction	Injection site injury
Injection site reaction	Injection site irritation
Injection site reaction	Injection site ischaemia
Injection site reaction	Injection site joint discomfort

Category	PT
Injection site reaction	Injection site joint effusion
Injection site reaction	Injection site joint erythema
Injection site reaction	Injection site joint infection
Injection site reaction	Injection site joint inflammation
Injection site reaction	Injection site joint movement impairment
Injection site reaction	Injection site joint pain
Injection site reaction	Injection site joint swelling
Injection site reaction	Injection site joint warmth
Injection site reaction	Injection site laceration
Injection site reaction	Injection site lymphadenopathy
Injection site reaction	Injection site macule
Injection site reaction	Injection site mass
Injection site reaction	Injection site movement impairment
Injection site reaction	Injection site necrosis
Injection site reaction	Injection site nerve damage
Injection site reaction	Injection site nodule
Injection site reaction	Injection site oedema
Injection site reaction	Injection site pain
Injection site reaction	Injection site pallor
Injection site reaction	Injection site papule
Injection site reaction	Injection site paraesthesia
Injection site reaction	Injection site phlebitis
Injection site reaction	Injection site photosensitivity reaction
Injection site reaction	Injection site plaque
Injection site reaction	Injection site pruritus
Injection site reaction	Injection site pustule
Injection site reaction	Injection site rash
Injection site reaction	Injection site reaction
Injection site reaction	Injection site recall reaction
Injection site reaction	Injection site scab
Injection site reaction	Injection site scar
Injection site reaction	Injection site streaking
Injection site reaction	Injection site swelling
Injection site reaction	Injection site thrombosis
Injection site reaction	Injection site ulcer
Injection site reaction	Injection site urticaria
Injection site reaction	Injection site vasculitis
Injection site reaction	Injection site vesicles
Injection site reaction	Injection site warmth
Injection site reaction	Malabsorption from injection site

Immunogenicity: based on relevant PTs in the narrow SMQs for “Hypersensitivity”,

Category	PT
Hypersensitivity	Acute generalised exanthematous pustulosis
Hypersensitivity	Administration site dermatitis
Hypersensitivity	Administration site eczema
Hypersensitivity	Administration site hypersensitivity
Hypersensitivity	Administration site rash
Hypersensitivity	Administration site recall reaction
Hypersensitivity	Administration site urticaria
Hypersensitivity	Administration site vasculitis
Hypersensitivity	Allergic bronchitis
Hypersensitivity	Allergic colitis
Hypersensitivity	Allergic cough
Hypersensitivity	Allergic cystitis
Hypersensitivity	Allergic eosinophilia
Hypersensitivity	Allergic gastroenteritis
Hypersensitivity	Allergic granulomatous angiitis
Hypersensitivity	Allergic hepatitis
Hypersensitivity	Allergic keratitis
Hypersensitivity	Allergic myocarditis
Hypersensitivity	Allergic oedema
Hypersensitivity	Allergic otitis externa
Hypersensitivity	Allergic otitis media
Hypersensitivity	Allergic pharyngitis
Hypersensitivity	Allergic respiratory disease
Hypersensitivity	Allergic respiratory symptom
Hypersensitivity	Allergic sinusitis
Hypersensitivity	Allergic transfusion reaction
Hypersensitivity	Allergy alert test positive
Hypersensitivity	Allergy test positive
Hypersensitivity	Allergy to immunoglobulin therapy
Hypersensitivity	Allergy to vaccine
Hypersensitivity	Alveolitis allergic
Hypersensitivity	Anaphylactic reaction
Hypersensitivity	Anaphylactic shock
Hypersensitivity	Anaphylactic transfusion reaction
Hypersensitivity	Anaphylactoid reaction
Hypersensitivity	Anaphylactoid shock
Hypersensitivity	Anaphylaxis treatment
Hypersensitivity	Angioedema

Category	PT
Hypersensitivity	Antiallergic therapy
Hypersensitivity	Antiendomysial antibody positive
Hypersensitivity	Anti-neutrophil cytoplasmic antibody positive vasculitis
Hypersensitivity	Application site dermatitis
Hypersensitivity	Application site eczema
Hypersensitivity	Application site hypersensitivity
Hypersensitivity	Application site rash
Hypersensitivity	Application site recall reaction
Hypersensitivity	Application site urticaria
Hypersensitivity	Application site vasculitis
Hypersensitivity	Arthritis allergic
Hypersensitivity	Atopy
Hypersensitivity	Blepharitis allergic
Hypersensitivity	Blood immunoglobulin E abnormal
Hypersensitivity	Blood immunoglobulin E increased
Hypersensitivity	Bromoderma
Hypersensitivity	Bronchospasm
Hypersensitivity	Catheter site dermatitis
Hypersensitivity	Catheter site eczema
Hypersensitivity	Catheter site hypersensitivity
Hypersensitivity	Catheter site rash
Hypersensitivity	Catheter site urticaria
Hypersensitivity	Catheter site vasculitis
Hypersensitivity	Chronic eosinophilic rhinosinusitis
Hypersensitivity	Chronic hyperplastic eosinophilic sinusitis
Hypersensitivity	Circulatory collapse
Hypersensitivity	Circumoral oedema
Hypersensitivity	Conjunctival oedema
Hypersensitivity	Conjunctivitis allergic
Hypersensitivity	Corneal oedema
Hypersensitivity	Cutaneous vasculitis
Hypersensitivity	Dennie-Morgan fold
Hypersensitivity	Dermatitis
Hypersensitivity	Dermatitis acneiform
Hypersensitivity	Dermatitis allergic
Hypersensitivity	Dermatitis atopic
Hypersensitivity	Dermatitis bullous
Hypersensitivity	Dermatitis contact
Hypersensitivity	Dermatitis exfoliative
Hypersensitivity	Dermatitis exfoliative generalised

Category	PT
Hypersensitivity	Dermatitis herpetiformis
Hypersensitivity	Dermatitis infected
Hypersensitivity	Dermatitis psoriasiform
Hypersensitivity	Distributive shock
Hypersensitivity	Documented hypersensitivity to administered product
Hypersensitivity	Drug cross-reactivity
Hypersensitivity	Drug eruption
Hypersensitivity	Drug hypersensitivity
Hypersensitivity	Drug provocation test
Hypersensitivity	Drug reaction with eosinophilia and systemic symptoms
Hypersensitivity	Eczema
Hypersensitivity	Eczema infantile
Hypersensitivity	Eczema nummular
Hypersensitivity	Eczema vaccinatum
Hypersensitivity	Eczema vesicular
Hypersensitivity	Eczema weeping
Hypersensitivity	Encephalitis allergic
Hypersensitivity	Encephalopathy allergic
Hypersensitivity	Epidermal necrosis
Hypersensitivity	Epidermolysis
Hypersensitivity	Epidermolysis bullosa
Hypersensitivity	Epiglottic oedema
Hypersensitivity	Erythema multiforme
Hypersensitivity	Erythema nodosum
Hypersensitivity	Exfoliative rash
Hypersensitivity	Eye allergy
Hypersensitivity	Eye oedema
Hypersensitivity	Eye swelling
Hypersensitivity	Eyelid oedema
Hypersensitivity	Face oedema
Hypersensitivity	Giant papillary conjunctivitis
Hypersensitivity	Gingival oedema
Hypersensitivity	Gingival swelling
Hypersensitivity	Gleich's syndrome
Hypersensitivity	Haemorrhagic urticaria
Hypersensitivity	Hand dermatitis
Hypersensitivity	Henoch-Schonlein purpura
Hypersensitivity	Henoch-Schonlein purpura nephritis
Hypersensitivity	Hereditary angioedema
Hypersensitivity	Hypersensitivity

Category	PT
Hypersensitivity	Hypersensitivity vasculitis
Hypersensitivity	Idiopathic urticaria
Hypersensitivity	Immediate post-injection reaction
Hypersensitivity	Immune thrombocytopenic purpura
Hypersensitivity	Immune tolerance induction
Hypersensitivity	Infusion site dermatitis
Hypersensitivity	Infusion site eczema
Hypersensitivity	Infusion site hypersensitivity
Hypersensitivity	Infusion site rash
Hypersensitivity	Infusion site recall reaction
Hypersensitivity	Infusion site urticaria
Hypersensitivity	Infusion site vasculitis
Hypersensitivity	Injection site dermatitis
Hypersensitivity	Injection site eczema
Hypersensitivity	Injection site hypersensitivity
Hypersensitivity	Injection site rash
Hypersensitivity	Injection site recall reaction
Hypersensitivity	Injection site urticaria
Hypersensitivity	Injection site vasculitis
Hypersensitivity	Instillation site hypersensitivity
Hypersensitivity	Instillation site rash
Hypersensitivity	Instillation site urticaria
Hypersensitivity	Interstitial granulomatous dermatitis
Hypersensitivity	Intestinal angioedema
Hypersensitivity	Iodine allergy
Hypersensitivity	Kaposi's varicelliform eruption
Hypersensitivity	Kounis syndrome
Hypersensitivity	Laryngeal oedema
Hypersensitivity	Laryngitis allergic
Hypersensitivity	Laryngospasm
Hypersensitivity	Laryngotracheal oedema
Hypersensitivity	Limbal swelling
Hypersensitivity	Lip oedema
Hypersensitivity	Lip swelling
Hypersensitivity	Mast cell degranulation present
Hypersensitivity	Mouth swelling
Hypersensitivity	Mucocutaneous rash
Hypersensitivity	Multiple allergies
Hypersensitivity	Nephritis allergic
Hypersensitivity	Nikolsky's sign

Category	PT
Hypersensitivity	Nodular rash
Hypersensitivity	Oculomucocutaneous syndrome
Hypersensitivity	Oculorespiratory syndrome
Hypersensitivity	Oedema mouth
Hypersensitivity	Oral allergy syndrome
Hypersensitivity	Oropharyngeal blistering
Hypersensitivity	Oropharyngeal spasm
Hypersensitivity	Oropharyngeal swelling
Hypersensitivity	Palatal oedema
Hypersensitivity	Palatal swelling
Hypersensitivity	Palisaded neutrophilic granulomatous dermatitis
Hypersensitivity	Palpable purpura
Hypersensitivity	Pathergy reaction
Hypersensitivity	Periorbital oedema
Hypersensitivity	Pharyngeal oedema
Hypersensitivity	Pruritus allergic
Hypersensitivity	Radioallergosorbent test positive
Hypersensitivity	Rash
Hypersensitivity	Rash erythematous
Hypersensitivity	Rash follicular
Hypersensitivity	Rash generalised
Hypersensitivity	Rash macular
Hypersensitivity	Rash maculo-papular
Hypersensitivity	Rash maculovesicular
Hypersensitivity	Rash morbilliform
Hypersensitivity	Rash neonatal
Hypersensitivity	Rash papulosquamous
Hypersensitivity	Rash pruritic
Hypersensitivity	Rash pustular
Hypersensitivity	Rash rubelliform
Hypersensitivity	Rash scarlatiniform
Hypersensitivity	Rash vesicular
Hypersensitivity	Reaction to azo-dyes
Hypersensitivity	Reaction to colouring
Hypersensitivity	Reaction to drug excipients
Hypersensitivity	Reaction to preservatives
Hypersensitivity	Red man syndrome
Hypersensitivity	Rhinitis allergic
Hypersensitivity	Scleral oedema
Hypersensitivity	Scleritis allergic

Category	PT
Hypersensitivity	Scrotal oedema
Hypersensitivity	Serum sickness
Hypersensitivity	Serum sickness-like reaction
Hypersensitivity	Shock
Hypersensitivity	Shock symptom
Hypersensitivity	Skin necrosis
Hypersensitivity	Skin reaction
Hypersensitivity	Skin test positive
Hypersensitivity	Solar urticaria
Hypersensitivity	Solvent sensitivity
Hypersensitivity	Stevens-Johnson syndrome
Hypersensitivity	Stoma site hypersensitivity
Hypersensitivity	Stoma site rash
Hypersensitivity	Swelling face
Hypersensitivity	Swollen tongue
Hypersensitivity	Tongue oedema
Hypersensitivity	Toxic epidermal necrolysis
Hypersensitivity	Toxic skin eruption
Hypersensitivity	Tracheal oedema
Hypersensitivity	Type I hypersensitivity
Hypersensitivity	Type II hypersensitivity
Hypersensitivity	Type III immune complex mediated reaction
Hypersensitivity	Type IV hypersensitivity reaction
Hypersensitivity	Urticaria
Hypersensitivity	Urticaria cholinergic
Hypersensitivity	Urticaria chronic
Hypersensitivity	Urticaria contact
Hypersensitivity	Urticaria papular
Hypersensitivity	Urticaria physical
Hypersensitivity	Urticaria pigmentosa
Hypersensitivity	Urticaria vesiculosa
Hypersensitivity	Vaginal exfoliation
Hypersensitivity	Vaginal ulceration
Hypersensitivity	Vasculitic rash
Hypersensitivity	Vessel puncture site rash
Hypersensitivity	Vulval ulceration
Hypersensitivity	Vulvovaginal rash
Hypersensitivity	Vulvovaginal ulceration

Hyperphosphataemia: based on selected PTs below

Category	PT
Hyperphosphataemia	Hyperphosphataemia
Hyperphosphataemia	Blood phosphorus increased

Ectopic mineralization: based on a MedDRA search of ‘calcification’

Category	PT
Ectopic calcification	Adrenal calcification
Ectopic calcification	Aortic calcification
Ectopic calcification	Aortic valve calcification
Ectopic calcification	Aortic valve sclerosis
Ectopic calcification	Articular calcification
Ectopic calcification	Bladder wall calcification
Ectopic calcification	Breast calcifications
Ectopic calcification	Bursa calcification
Ectopic calcification	Calcific deposits removal
Ectopic calcification	Calcification metastatic
Ectopic calcification	Calcification of muscle
Ectopic calcification	Calcinosis
Ectopic calcification	Calculus bladder
Ectopic calcification	Calculus prostatic
Ectopic calcification	Calculus ureteric
Ectopic calcification	Calculus urethral
Ectopic calcification	Calculus urinary
Ectopic calcification	Cardiac valve sclerosis
Ectopic calcification	Cerebral calcification
Ectopic calcification	Chondrocalcinosis
Ectopic calcification	Chondrocalcinosis pyrophosphate
Ectopic calcification	Cutaneous calcification
Ectopic calcification	Dystrophic calcification
Ectopic calcification	Heart valve calcification
Ectopic calcification	Heart valve stenosis
Ectopic calcification	Hepatic calcification
Ectopic calcification	Intervertebral disc calcification
